5.2 ANALYSIS OF PRIMARY EFFICACY ENDPOINT (AIM 1)

The primary analysis will be intent-to-treat (ITT). Section 6.0 discuss details of how missing data and intercurrent events (ICEs) will be analyzed. We will test the hypothesis that the change in HbA1c from baseline to 6 months differed between FAM-ACT and individual focused arm.

We will first graphically examine how HbA1c change over time. We will then conduct our main analyses using linear mixed-effects models that include repeated measures at baseline, 6 months, and 12 months. To evaluate the effect of the intervention over time, we will include time in the model plus an interaction term for time x intervention arm. We will also explore models with time as a categorical instead of continuous variable and use the model that fits best, based on Akaike's Information and Schwarz's Bayesian Criteria. The primary hypotheses (change from baseline to 6 months) will be tested using appropriate linear contrasts. Treatment effect estimates will be presented along with 95% confidence intervals. The model will be adjusted for our design variables (baseline HbA1c and whether the patient and SP live together), baseline insulin use, and age. If baseline HbA1c and insulin use are highly correlated, we will prioritize HbA1c in the primary model and adjust for insulin use in sensitivity analyses.

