This is a multicenter protocol for the FAM-ACT Study. All participant interaction and data collection will be completed at a U.S. Federally Qualified Health Center (FQHC) in Detroit, Michigan. The University of Pittsburgh PI will be responsible for study oversight, data management, and analysis. While there are two locations for research activities, they will not follow the same protocol. This protocol outlines the FQHC and University of Pittsburgh's roles.

PROTOCOL ADAPTATIONS RELATED TO COVID-19 PANDEMIC

The intervention initially had been designed to span 12 months as described in the 'original protocol' (v 1.0, May 13, 2019). The original protocol was used for the first 77 patient-support person dyads who enrolled in the study prior to March 2020, when the COVID-19 pandemic reached the United States and limits were placed on the conduct of in-person research activities. In response to the pandemic, several modifications were made to the protocol—including reducing the length of the intervention to 6 months—both to ensure the safety of study participants and research staff as well as to compensate for a temporary pause in enrollment due to pandemic-related restrictions on recruitment activities ('adapted protocol'). Differences between the two protocols are summarized in **Appendix 1**. The adapted protocol was put into effect in February 2021, when recruitment activities were permitted to restart, and will remain in effect throughout the duration of the study. This document describes the protocol that has been used since February 2021. For additional detail on the adaptations that were made to the protocol, see our 2022 publication in *Trials*¹.

RESEARCH PROTOCOL ABSTRACT

Diabetes self-management interventions have struggled to deliver relevant, effective, and sustainable support for at-risk adults with diabetes to improve key diabetes self-management behaviors, become more activated participants in healthcare and reduce diabetes complications. One largely untapped resource for this support is patients' family and friends. Three out of four adults with diabetes reach out to an unpaid family member or friend (a 'Support Person') for ongoing help with diabetes management.

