1. Take part in a one-hour introductory session designed to provide an overview of diabetes complications, how to set goals, and prepare for/participate in primary care appointments. During this session, the patient's diabetes complication risk profile will be discussed.
2. Be invited to 4-6 group diabetes self-management education sessions to be held at the FQHC or online using Pitt's HIPAA-compliant Zoom environment. In-person sessions at the FQHC will last approximately 1.5 hours whereas online sessions will be designed to last approximately 45 minutes. American Diabetes Association-approved 'Conversation Maps' will be used as a tool for patient education when feasible.
3. Complete an additional survey assessment and lab measures (blood pressure, weight and fingerstick blood HbA1c) with the study RA 6-months after enrollment. The SP will only complete one additional survey assessment 6 months after enrollment⁴. (*Some patients in both arms may be contacted 12-15 months post-enrollment to complete an additional assessment if the study still is active at the time that assessment window opens.*)
4. Receive care management contacts with a CHW every 2-4 weeks either in person or remotely (when necessary). The CHW will talk with the patient for approximately 20 minutes each time for the remainder of the 6-month enrollment period.
5. Patients who enrolled in the study prior to August 2020 will be contacted by phone for an additional, optional "FAM-ACT COVID" survey. The purpose of this survey is to determine how the events of the COVID-19 pandemic have affected patients' ability to participate in the intervention, and to care for their diabetes

PROGRAM B: SP-FOCUSED DSMES (FAM-ACT)

The FAM-ACT intervention will include patients and their SP together as much as possible. In this arm, the enrolled FQHC Patient and their SP (referred to as a dyad) will:

1. Take part in a one-hour introductory session designed to provide an overview of diabetes complications, ways the SP and patient can work together positively, and ways to set "SMART" health goals. During this session, results of a diabetes complication risk profile are discussed with the patient and support person and the dyad learns how to set goals together.

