2. Be invited to 4-6 family-focused, group diabetes self-management education sessions to be held at the FQHC or online using Pitt's HIPAA-compliant Zoom environment. In-person sessions at FQHC will last approximately 2 hours each, whereas online sessions will be designed to last approximately 1 hour. American Diabetes Association-approved "Conversation Maps" will be used as a tool for providing patient education when

⁴ In both arms, a +3 month assessment window will be permitted for both patient and SP assessments.

feasible. Additional family-focused topics will be discussed, such as patient-SP communication and SP roles in helping patients participate actively in healthcare provider appointments.

3. Complete additional survey assessments and lab measures (blood pressure, weight, fingerstick A1c, and lipids) with the study RA 6-months after enrollment. The SP will only complete one additional survey assessment 6-months after enrollment.
4. Receive care management contacts with a CHW every 2-4 weeks either in person or remotely (when necessary). The CHW will talk with the dyad for approximately 20 minutes each time for the remainder of the 6-month enrollment period.
5. Patients who enrolled in prior to August 2020 will be contacted by phone for an additional, optional "FAM-ACT COVID" survey. The purpose of this survey is to determine how the events of the COVID-19 pandemic have affected participants' ability to participate in the intervention, and to care for their diabetes

Additionally, the patient will have their FQHC electronic chart reviewed for diabetes-related visit, lab, and medication information for the period from 12 months prior to 24 months following their study enrollment date.

INTERVENTION PROCEDURES CONDUCTED IN BOTH STUDY ARMS

A trained and supervised CHW, CHW Manager, and/or RA at the FQHC will conduct all research participant contacts. Contacts at the FQHC will be supervised by the CHW Manager and Site PI. In-person diabetes self-management education group sessions will take place in a large conference room with other FQHC patients present. Online group sessions will be attended by study participants and the CHW(s). A study RA also may be present to assist with technical issues. Participant assessments will be completed in a private location at the FQHC or remotely via phone/video call or Zoom.

STUDY MEASURES

PATIENT MEASURES

Hemoglobin A1c (HbA1c)

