Smoking status	HB	Global Adult Tobacco Survey (GATS)(16)	X	X	X
Smoking - # cigarettes/day	HB	Global Adult Tobacco Survey (GATS)	X	X	X
Patient's General Perceived Social Support	GSS	ENRICHED Social Support Instrument (ESSI)(17)	X	X	
Patient overall satisfaction with SP support for diabetes	PSP	Patient overall satisfaction with SP support items created for CO-IMPACT Study(18) ^b	X	X	X
Patient perceived supportive vs. non-supportive SP behaviors	PSP		X	X	X
Autonomy support ("supportive behaviors")		Important Other Climate Questionnaire (IOCQ)(19)			
Non-supportive behaviors		3 items created for this study ^c			
SP Helps with Medical Visits	SPBA	Items created for CO-IMPACT Study(18)	X	X	X
SP Roles in Patient Diabetes Management Care	SPBA	Items created for CO-IMPACT Study(18) ^d	X	X	X
Impact of COVID on ability to manage diabetes	COVID-19 impact	Single item created for study ^e		X	X

BL, baseline; 6M, 6-month follow up; 12M, 12 month follow up; CO-IMPACT; Caring Others Increasing Engagement in Patient Aligned Care Teams Study; ENRICHED, Enhancing Recovery in Coronary Heart Disease Study; GSS, general social support; HB, health behaviors; PBD, psychological behavior determinants; PEH, patient engagement in healthcare PSP, patient perceptions of SP help; SP, support person; SRBA, SP roles, behaviors and attitudes; SMB, self-management behaviors

Bold type, change in measure from baseline to 6-months will be examined as a secondary outcome (see Study Analysis Plan, SAP)

^aPer the COVID-adapted protocol, 12-month assessments will be completed only if study timeline permits.

^bTwo items assessing patient's satisfaction with the support they receive from their SP and whether they feel like they would be worse off without their SP's help with their diabetes care

^cNon-supportive behaviors will be assessed with 3 items structured similarly to the IOCQ items addressing SP irritation, criticism and argumentativeness.

^dExample roles include suggesting questions prior to patients' health care appointments, accompanying the patient in the exam room, discussing the visit after it has ended

^e"In the last six months, how have the COVID pandemic or social distancing rules affected your ability to manage your diabetes?" (5-point scale, 1-much harder to 5-much easier)

SUPPORT PERSON MEASURES

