3.1 SAMPLE SIZE AND POWER CONSIDERATIONS

We powered our study to detect a clinically meaningful difference in our primary outcome HbA1c at 6 months (Aim 1) based on a linear mixed model with intervention arm, linear time (0, 6, and 12 months), and interaction between intervention arm and time. We assumed that, due to randomization, the mean difference at baseline is zero and that the intervention effect is represented by the between group difference in time slope (captured by the intervention arm by time interaction), or equivalently, differences at follow-up time points. All calculations assumed at least 80% power and two-sided tests at level $\alpha = 0.05$ using the R package `longpower` (1). The standard deviation of HbA1c at any given time point was estimated to be between 1.5% to 2.2% based on previous studies (2–5). The correlation between timepoints, as measured by the intra-class correlation coefficient (ICC) ranged from 0.5 to 0.7 based on the RCT data at the Federally Qualified Health Center (FQHC) where the study is being conducted. Table 1 shows the total sample size required for various intervention effects.

Table 1: Total sample size (N) required for different intervention effects assuming a range of ICCs and SDs for *HbA1c*

SLOPE DIFFERENCE	MEAN DIFFERENCE AT 6 MONTHS	ICC	SD			
			1.50%	1.75%	2.00%	2.20%
0.067	0.40%	0.5	442	601	785	950
		0.6	354	481	628	760
		0.7	265	361	471	570
0.083	0.50%	0.5	283	385	503	608
		0.6	227	308	402	487
		0.7	170	231	302	365
0.010	0.60%	0.5	197	268	349	423
		0.6	157	214	280	338
		0.7	118	161	210	254
0.116	0.70%	0.5	145	197	257	311
		0.6	116	157	206	249
		0.7	87	118	154	187

To detect a 6-month mean difference of 0.6% in HbA1c, the total sample size required is 214 (highlighted in table above). We chose this sample size based detecting a clinically meaningful effect while considering the study size recruitment feasibility. The detectable effect is similar to what was observed in prior studies. We assumed an HbA1c standard deviation (SD=1.75%) and ICC (ICC=0.6) within the range of potential values reported in the

literature. If these estimates were conservative (i.e., if true SD=1.5% and true ICC=0.7), our sample size achieves at least 80% power to detect mean difference as small as 0.4%.

Anticipating 20% attrition based on the rate observed in prior 6-month and 12-month RCTs at the FQHC, we propose to recruit a total of 268 dyads (134 per group).

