4.0 STUDY ENDPOINTS AND COVARIATES

4.1 PRIMARY ENDPOINT

The primary outcome is the change in patient glycemic control from baseline to 6 months. Glycemic control is measured by HbA1c in %.

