6.2 INTERCURRENT EVENTS

We identified and evaluated all plausible strategies for each ICE in this study in line with the ICH E9 R1 guidelines. For each ICE, Table 2 below shows the strategy we selected (primary highlighted in green, supplemental highlighted in yellow) based on what most aligns with our clinical question of interest.

Table 2. Strategies for handling intercurrent events

ICE	STRATEGY	DESCRIPTION
Home A1c (instead of clinic)	Composite	
 - Home A1c will be analyzed if clinic A1c is unavailable.
	Hypothetical	
 - Home A1c will be treated as missing outcome data. Mixed modeling will project what would have been the clinic A1c at the timepoint from patient's available clinic A1c (e.g., BL, 6mo) of from similar patients.
Phone survey (instead of in-person)	Composite	
 - Phone survey will be analyzed if in-person survey is unavailable.
	Hypothetical	
 - Phone survey responses will not be used and treated as missing data. Mixed modeling will project what would have been the in-person survey response at the timepoint from patient's available in-person survey responses (e.g., BL, 6mo) of from similar patients.
Wider outcome assessment window	Hypothetical	
 - This will be more applicable when time enters the model as continuous variable. - Mixed model will project what would have been the outcome at the exact timepoint it should have been measured based on existing outcome data or trajectory or from similar patients.
	Composite	
 - This will be more applicable when time is entered into the model as categorical variable. - Data collected within the expanded window will be analyzed along with those collected in the original window at the timepoint.
Noncompliance	Treatment policy	
 - Observed outcomes after non-compliance will be used in the analysis. - This is the pure ITT approach.
	Principal Stratification	
 - Baseline characteristics will be used to identify the latent subgroup of compliers (in both intervention and control groups). - Patients observed or predicted to be compliers will be used in the analysis to estimate the complier average causal effect (CACE).

ICE	STRATEGY	DESCRIPTION

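### The primary 6-month HbA1c effect may come from either a linear-time or a categorical-time model, chosen by AIC and BIC on the trial's own outcomes, with no rule if the two criteria disagree

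*SAP*

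**What the plan says.** SAP 4.1 fixes the endpoint: "The primary outcome is the change in patient glycemic control from baseline to 6 months".

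SAP 5.2 fits HbA1c at baseline, 6 and 12 months with time and a time-by-arm interaction. It continues: "We will also explore models with time as a categorical instead of continuous variable and use the model that fits best", using the Akaike and Schwarz criteria. The primary hypothesis is tested by contrasts from the selected model. The SAP does not rank the two criteria, name a default form, or say whether likelihoods are ML or REML. The general assumption checks in 5.1 do not settle any of this.

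SAP 3.1 says the trial was powered "based on a linear mixed model with intervention arm, linear time (0, 6, and 12 months), and interaction between intervention arm and time".

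The 12-month data will be partial. Protocol Table 1, footnote a, says "12-month assessments will be completed only if study timeline permits", and Program A, item 3, says "Some patients in both arms may be contacted 12-15 months post-enrollment to complete an additional assessment if the study still is active". Footnote 4 adds that "a +3 month assessment window will be permitted for both patient and SP assessments".

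Two intervention lengths are pooled. On enrolment before the pandemic: "The original protocol was used for the first 77 patient-support person dyads who enrolled in the study prior to March 2020". Appendix 1 records that those dyads were planned for 12 months of intervention and later ones for 6.

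**The concern.** Choosing between time forms by overall fit across three visits does not ensure an unbiased contrast at one of them. A straight line through months 0, 6 and 12 lets the 12-month values pull the 6-month estimate. The adapted intervention ends at month 6, so an effect that plateaus or wanes afterwards is plausible. For the first 77 dyads, continued growth is also plausible.

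Two things are at stake. The reported 6-month effect may be biased, with a 95% interval that covers too seldom. And because AIC and BIC penalise the two extra parameters very differently, the primary result may depend on a choice between criteria that nobody has written down.

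**Working it through.** **Inputs from SAP 3.1.** SD 1.75, ICC 0.6, effect 0.6 at 6 months, 214 completers, 20% attrition, 268 randomised 1:1 (HbA1c in percentage points throughout).

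**Assumptions, not in the documents.** 12-month data in 15 / 29 / 50% of 6-month completers (29% is 77/268); various control trajectories; 12-month data missing completely at random; enrolment wave ignored.

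**1. The plan's own figure.** Under compound symmetry, N = 4(z₀.₉₇₅ + z₀.₈₀)² SD²(1 − ICC) / (Sxx × slope²).
- Visits 0 and 6: Sxx = 18, slope 0.6/6 = 0.1 per month. N = 4 × 7.849 × 3.0625 × 0.4 / 0.18 = 213.7, i.e. 214. (Table 1 prints this slope as 0.010; 0.1 is what its 0.60% label implies.)
- Visits 0, 6 and 12 at slope 0.1: Sxx = 72, N = 53.4.
- Visits 0, 6 and 12 at slope 0.05 also give 213.7, but then 0.6 is the 12-month difference, contrary to the table's label.

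As labelled, 214 is the two-visit figure. At 214 completers the two-visit contrast has SE √(8 × 3.0625 × 0.4 / 214) = 0.214 and power 80%.

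**2. What linear time estimates.** By generalised least squares (268 randomised, 20% with baseline only), the linear 6-month effect is w × (6-month effect) + (1 − w) × (half the 12-month effect). For a sustained effect of 0.60:

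| 12-month availability | w | Linear estimate | SE, linear | SE, categorical |
|---|---|---|---|---|
| 15% | 0.57 | 0.47 | 0.172 | 0.209 |
| 29% | 0.37 | 0.41 | 0.151 | 0.209 |
| 50% | 0.20 | 0.36 | 0.131 | 0.209 |

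For example, at 29%: 0.37 × 0.60 + 0.63 × 0.30 = 0.41. Categorical time gives 0.60 in each row.

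**3. Why the criteria disagree.** The forms differ by two fixed effects. AIC takes categorical time when the likelihood-ratio statistic exceeds 4. BIC needs more than 2 ln n: 11.2 with n = 268 patients, or 12.6 with n = 544 observations (268 + 214 + 62, at 29% availability).

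**4. Performance under selection.** Simulation by maximum likelihood with compound symmetry, 2,000 trials per scenario (Monte Carlo SE up to 1.1 points), no covariates, each criterion applied alone. BIC ranges reflect counting n as patients or observations. Effect 0.6 at months 6 and 12, 29% availability:

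| Control fall, held | AIC picks linear | BIC picks linear | Criteria disagree | Coverage, AIC | Coverage, BIC |
|---|---|---|---|---|---|
| 0 | 45% | 88–92% | 44–48% | 86% | 77–78% |
| 0.25 | 18% | 68–76% | 50–58% | 91% | 80–81% |
| 0.5 | 3% | 32–39% | 29–36% | 95% | 88–89% |
| 0.75 | 0.5% | 7–10% | 7–10% | 94% | 93% |
| 1.0 | 0% | 0.4–1% | 0.4–1% | 96% | 96% |

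Categorical time fixed in advance covers 94–96%, with power 78–84%. Across 15–50% availability with flat controls, coverage is 80–90% (AIC) and 58–88% (BIC).

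**5. Other scenarios at 29%.**
- Effect halves by month 12, flat controls: coverage 88% (AIC), 65–67% (BIC); power under BIC 65–67%, against 81% for categorical time.
- Effect grows to 0.9 by month 12, flat controls: coverage 89% (AIC), 90% (BIC).
- No effect at either visit: rejection 6–8% (AIC), 6% (BIC), 6% (categorical).
- Visits spread evenly over 6–9 and 12–15 months, actual times in the linear model: linear time gives 0.36 for a sustained 0.60, and 0.47 even with no 12-month data. With controls falling 0.5, coverage is 92% (AIC) and 71–75% (BIC).

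**The case against.** The strongest reply is that the damage rests on assumed trajectories. The comparator is an active programme and most patients qualify on raised HbA1c, so some fall in the control arm is likely. That fall is what steers both criteria to categorical time: AIC coverage is already nominal at a fall of 0.5. With a sustained effect the bias is toward the null and power is kept, and type I error under a full null is close to that of categorical time. This stands. It limits the size of the problem and makes it mainly one of estimation, but it does not supply the missing rule.

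Second, if 12-month data come mainly from the first 77 dyads, whose intervention was planned for 12 months, the effect may keep growing. The harm then shrinks and fixing categorical time has a price: with growth to 0.9 and flat controls, selection has power of about 89–92%, against about 80% for categorical time. This also stands, as a cost of the fix. The extra power comes from using 12-month information to answer a 6-month question.

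Third, when baseline HbA1c is both an outcome and a covariate, as 5.2 can be read, fixed categorical time covers only 92–93%. Part of the shortfall in those runs therefore has another cause. The additional loss from selection remains: with flat controls, coverage there is 83% (AIC) and 68–70% (BIC).

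**Conclusion.** The concern holds. That the form of the primary model is left to the outcome data, with two criteria and no tie-break, is plain from SAP 5.2 and needs no assumption. That linear time misses the stated endpoint, unless the effect doubles by month 12 or there are no 12-month data, follows algebraically for visits on schedule.

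The size is conditional. With a sustained effect and 29% availability, the loss of coverage is large if controls stay near flat, moderate under BIC if they fall 0.5 and hold, and essentially absent if they fall 1.0 and hold. Confidence is high on the missing rule and moderate on the magnitude. It should be fixed before outcome data are analysed.

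**What to change.** In SAP 5.2, replace the selection sentence with: *Visit (baseline, 6, 12 months) will be categorical. The primary contrast is the arm difference in change from baseline to 6 months. A linear-time model will be reported as a sensitivity analysis.*

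Two smaller alignments follow:
- **SAP 3.1:** state that Table 1 and N = 214 correspond to the two-visit (0 and 6 month) contrast, since the text describes three visits.
- **SAP 6.2, Table 2, wider-window row:** check that the strategy marked primary is the one the table ties to categorical time. The coding ("primary highlighted in green, supplemental highlighted in yellow") is not visible in the text available to us, so this is a check and not a defect.

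The cost is a sentence in each of 5.2 and 3.1 and the check, with no extra patients or data. There are three statistical downsides:
- The categorical interval is wider than the linear one by 22 / 38 / 60% at 15 / 29 / 50% availability (0.209 divided by 0.172, 0.151 and 0.131).
- Power is forgone if the effect truly keeps growing after month 6.
- With the 3-month window, the categorical 6-month value averages over visits at 6–9 months. If a 0.6 effect halves linearly by month 12 and visits spread evenly, that average is 0.6 − 0.05 × 1.5 = 0.525.

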4.2 SECONDARY ENDPOINTS

Secondary outcome measures include the following:

- Change in HbA1c from baseline to 12 months
- Change in blood pressure from baseline to 6 months and to 12 months
 - Blood pressure will be measured by an automatic blood pressure monitor, taking the average of two readings taken 2 minutes apart. We will average the SBP at 6 months and 12 months and compare to SBP at baseline.
- Change from baseline to 6 months and to 12 months in diabetes distress in patient and in SP
 - The Problem Areas in Diabetes (PAID-5) Scale is comprised of 5 closed-ended items with response options ranging from 0 ('not a problem') to 4 ('serious problem'). The scale's 5 items will be summed to create a total score with a range of 0 to 20. A total score of ≥ 8 indicates possible diabetes-related emotional distress that warrants further assessment, with higher scores suggesting greater diabetes-related emotional distress.
- Change from baseline to 6 months in diabetes self-care behaviors in patient - including domains of diet, exercise, blood sugar testing, blood pressure checking, foot care and medication taking.
 - The Summary of Diabetes Self-Care Activities (SDSCA) is a brief self-report instrument for measuring levels of self-management across different domains of the diabetes regimen. Our study will score results within each domain by averaging the item scores (each ranging from 0-7) within each domain.
- Change from baseline to 6 months in self-efficacy of patient and of SP
 - The Self-Efficacy for Managing Chronic Diseases Scale is comprised of 5 items asking respondents to indicate how confident they are that they regularly can perform tasks related to their diabetes management. Responses range from 0 to 10, with higher numbers indicating greater self-efficacy.
- Change from baseline to 6 months in patient activation
 - The Patient Activation Measure (PAM)-10 uses a 4-point scale (1=strongly disagree to 4=strongly agree), where respondents indicate the extent to which statements related to being ready, willing and able to manage their health and health care accurately describe them. Responses are summed to create a total score with higher numbers indicating greater activation.
- Patient perceived overall satisfaction with SP support for diabetes from baseline to 6 months

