5.0 STATISTICAL METHODS

5.1 GENERAL APPROACH

For all analyses, the overall level of significance will be set to $\alpha=0.05$. To achieve maximum power for the primary endpoint, and because analyses involving the secondary outcomes, mediation, and moderation are considered hypothesis generating, no adjustment for multiple testing will be used. Data analyses will be performed using SAS v9.4 (SAS Institute, Cary, NC) or the latest version of R (currently 4.2.2; <https://cran.r-project.org/>).

We will examine baseline data for prognostically important differences across the two study groups. All main outcome analyses will be conducted at the individual patient level, with treatment group as the primary grouping factor. Prior to hypothesis testing, data will be examined using standard univariate descriptive measures and bivariate statistical measures of association, as well as graphical displays. Statistical assumptions required for the methods of analysis outlined in this section will be rigorously tested. The failure of statistical assumptions necessary for the techniques planned will be addressed in one of the following ways: 1) a different method of analysis will be used (e.g., non-parametric tests versus parametric tests); or 2) the data will be appropriately transformed to a distribution that meets the assumptions of the proposed statistical test.

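### Protocol version is not in the primary model, and the single 12-month HbA1c contrast mixes patients at the planned end of a 12-month programme with patients about six months past a 6-month one

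*SAP*

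**What the plan says.** **Two versions.** The Protocol's COVID-19 section states: "The original protocol was used for the first 77 patient-support person dyads", all enrolled before March 2020. The adapted version took effect in February 2021. The planned total is 268 dyads (SAP 3.1).

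**What version changes** (Protocol Appendix 1, Intervention Arms and footnote 4, Table 1):

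| Feature | Original | Adapted |
|---|---|---|
| Planned programme | 12 months; sessions in the first six, then CHW care-management contacts | 6 months |
| HbA1c entry threshold | 8.0% or above (or a blood-pressure route) | 7.5% or above |
| HbA1c windows | 5–7 and 11–13 months | 6–9 and 12–15 months |
| 12-month visit | planned for all | "12-month assessments will be completed only if study timeline permits" |

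The current inclusion criteria still list a blood-pressure route that Appendix 1 says was removed. Those passages must be reconciled, but this point does not depend on it.

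**The model.** SAP 5.2 fits a mixed model to baseline, 6 and 12 months: "The model will be adjusted for our design variables (baseline HbA1c and whether the patient and SP live together), baseline insulin use, and age". There is no version or period term. Time may be linear or categorical, whichever fits better.

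**The 12-month endpoint.** SAP 4.2 lists one secondary endpoint, "Change in HbA1c from baseline to 12 months", with no split by version.

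**Related analyses.** SAP 5.4 names enrolment before or after March 2020 as a moderator, crossed with group by time. SAP 6.4 adds a group by COVID-period interaction. Both give stratum estimates only if the interaction is significant.

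**The concern.** Version is known at randomisation, may affect the HbA1c trajectory, and is the main planned determinant of who has a 12-month value. SAP 6.1 relies on the mixed model being valid under missing-at-random. That assumption is easier to defend when the model contains the variable that governs planned availability.

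The 12-month contrast has a further difficulty of meaning. An original-version patient is then at the planned end of the programme, after six months of care-management contacts. An adapted-version patient is about six months past the end. A pooled contrast describes neither group. Its weights depend on how many adapted patients' windows open while funding lasts, so the same trial could report different 12-month effects for administrative reasons alone.

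**Working it through.** **Inputs from the documents.** SD 1.75, ICC 0.6, difference 0.6, two-sided 0.05, 80% power, 20% attrition, 268 dyads (SAP 3.1); 77 original-version dyads (Protocol).

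**Inputs assumed.** The documents give no between-version difference in mean change, no share of adapted patients reaching 12 months and no 12-month effects. Ranges are shown. Attrition of 20% is applied to both versions.

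**1. The plan's own figure.** The SAP states: "To detect a 6-month mean difference of 0.6% in HbA1c, the total sample size required is 214".
- SD of change = 1.75 × √(2 × (1 − 0.6)) = 1.565.
- Total N = 4 × (1.565 × (1.960 + 0.842) / 0.6)² = 213.7, so 107 per arm and 214 in total. This reproduces the figure from baseline and 6 months.
- 214 / 0.8 = 267.5, so 268.

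**2. Cohort sizes.** 77 original (28.7%) and 268 − 77 = 191 adapted (71.3%). After attrition: 77 × 0.8 = 61.6 and 191 × 0.8 = 152.8.

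**3. Precision lost by omitting version.** If mean change differs by D between versions, the variance of change rises from 1.565² = 2.45 by 0.287 × 0.713 × D² = 0.205 × D².

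| D (assumed) | Variance increase | N needed | Power at 214 |
|---|---|---|---|
| 0 | none | 214 | 80.1% |
| 0.25 | 0.5% | 215 | 79.9% |
| 0.5 | 2.1% | 218 | 79.2% |
| 1.0 | 8.4% | 232 | 76.8% |

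D here means the difference remaining after the covariates already in the model.

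**4. The pooled 12-month contrast.** Let f be the share of adapted patients with a 12-month visit. The original-version weight is w = 61.6 / (61.6 + 152.8 f), and the pooled effect is roughly 0.6w + e(1 − w), where 0.6 is the assumed original-version effect and e the assumed adapted-version effect.

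| f | w | Pooled, e = 0.3 | Pooled, e = 0 |
|---|---|---|---|
| 0.25 | 62% | 0.49 | 0.37 |
| 0.5 | 45% | 0.43 | 0.27 |
| 1.0 | 29% | 0.39 | 0.17 |

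If the two effects are equal, pooling does not change the value. A mixed model will not weight exactly this way, but the direction is the same.

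**5. Power of the interaction test at 6 months.**
- SE = 1.565 × √(4/61.6 + 4/152.8) = 0.47.
- Difference detectable with 80% power: 2.80 × 0.4725 = 1.32 points.
- If the effects differ by 0.6: Φ(0.6/0.4725 − 1.96) = 25% power.

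With fewer adapted patients at 12 months the test is weaker still.

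**6. Precision of version-specific 12-month estimates.** Half-width of the 95% interval = 1.96 × 1.565 × √(4/n), taking the same SD of change at 12 months:
- Original, n = 62: 0.78.
- Adapted, n = 38 (f = 0.25): 1.00.
- Adapted, n = 153 (f = 1): 0.50.

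**7. Dependence on how time is coded.** With categorical time, a true 6-month effect of 0.6 is recovered whatever f is. With linear time and a true effect of 0.6 at both 6 and 12 months, generalised least squares with SD 1.75 and ICC 0.6 gives a fitted 6-month contrast of 0.41, 0.33 or 0.30 at f = 0, 0.5 or 1.

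**The case against.** A reader might infer more than the documents support:

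- **That version confounds the primary comparison.** Dyads are randomised 1:1, and the optional 12-month visit is offered in both arms subject to the timeline. Version is not a confounder, and missing adapted-version visits are mainly administrative. This objection stands.
- **That the endpoint pools two different time points.** Both cohorts are measured about 12 months from baseline, in overlapping windows. What differs is position relative to the programme.
- **That the SAP ignores version.** On the Protocol's dates, the March 2020 split coincides with version, and SAP 5.4 already has the arm by time by period model. SAP 6.2 treats wider windows, home HbA1c, class delays and Zoom delivery as intercurrent events. The changed threshold acts at least partly through baseline HbA1c, which is adjusted for. What is missing is a version term in the main model and unconditional reporting by version.
- **That the versions are very different treatments.** Appendix 1 says most original-version contacts fell in the first six months. Nor do the documents say that every original-version dyad completed 12 months, or that all their visits kept to the original windows.

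Two further objections are fair. The 12-month endpoint is secondary, and SAP 5.1 calls secondary analyses hypothesis generating. Version-specific estimates will also be too imprecise to tell 0.6 from 0.3. Both limit the weight of the point, but neither makes the pooled figure easier to interpret.

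**Conclusion.** The point holds as a minor one. Version is absent from the primary model although it is known at baseline and governs planned 12-month availability. For the 6-month comparison with categorical time, the cost is precision only: between 0.2 and 3.3 percentage points of power over the assumed range of 0.25 to 1.0 point.

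The 12-month HbA1c contrast is the weaker result. Its value can shift with visit completion (0.49 to 0.39 in the 0.6 and 0.3 example), and the existing rule would usually leave only the pooled value, since the interaction test has about 25% power for a 0.6 difference at 6 months. These figures rest on assumed effects and visit rates. They show how the estimate behaves and do not predict the result. The SAP's N is unaffected.

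**What to change.** 1. Add protocol version and version by time to the SAP 5.2 model. This improves precision slightly and supports missing-at-random. It does not separate the 12-month effects, because one arm by time effect remains.
2. Use the arm by time by version model already available under SAP 5.4 to report the 12-month HbA1c contrast by version, with confidence intervals, regardless of the interaction test. Label the estimates as planned end of programme and about six months after planned end, and note that the documents do not say all original-version dyads completed 12 months.
3. Align SAP 6.4, which omits time from its interaction, with SAP 5.4.
4. Fix time as categorical for the primary contrast. Adding version does not remove the linear-time problem in step 7 of the working.

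The cost is a few degrees of freedom and some SAP wording. Version-specific 12-month intervals will be wide: about ±0.8 point with 62 original-version patients and ±1.0 with 38 adapted ones. They should be presented as descriptive.
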